8.1.3 Storage Requirements

The recommended storage conditions, and expiry date where required, are stated on the product label.

8.1.4 Route of administration

The route of administration is oral.

Drug-drug interactions/ Drug-food interactions

Drugs that are strong inhibitors or inducers of CYP3A or CYP2C8, Pgp or Bcrp transporters, are prohibited because they may increase or decrease, respectively Dabrafenib concentrations (Appendix B). Mild or moderate inhibitor/inducers of these enzymes/transporters should be used with caution.

Dabrafenib solubility is pH-dependent with decreased solubility at higher pH. Drugs such as proton pump inhibitors that inhibit gastric acid secretion to elevate gastric pH may decrease the solubility of dabrafenib and reduce its bioavailability. No clinical study has been conducted to evaluate the effect of pH on dabrafenib pharmacokinetics. In adhoc analysis, no differences in Cmax and AUC were noted between subjects who reported taking pH-elevating products relative to other subjects. Due to the theoretical risk that pH-elevating agents may decrease oral bioavailability and exposure to dabrafenib, these medicinal products that increase gastric pH should be used with caution when administered with dabrafenib. See section 5.2.2 re: supportive care when necessary.

Patients should take Dabrafenib at least one hour prior to or two hours after a meal due to a potential food effect on Dabrafenib absorption. Subjects should abstain from ingestion of Seville oranges, grapefruit or grapefruit juice, pummelos, or exotic citrus fruits or grapefruit hybrids while on the study, and avoid ingestion of such fruit(s) for at least 24 hours prior to the start of the first dose due to potential increased plasma Dabrafenib concentrations due to inhibition of intestinal CYP3A4.

8.2 Trametinib (MEKi)

8.2.1 Pharmaceutical Description

Trametinib Tablets are supplied as, 0.5 mg, and 2 mg (as free base) tablets for oral administration. Trametinib

Trametinib Tablets, 0.5 mg are yellow, modified oval, biconvex, film-coated tablets.

Trametinib Tablets, 2 mg (as free base) are pink, round, biconvex, film-coated tablets. Trametinib Tablets are packaged into a high density polyethylene (HDPE) bottle that contains desiccant with a child-resistant closure that includes an induction seal liner.

8.2.2 Physical and Chemical Properties of the Drug

Novartis Code: TMT212-NXA The suffix NXA denotes the dimethyl sulfoxide solvate form.

Approved Name: Mekinist (Trametinib) dimethyl sulfoxide (USAN)

Other Names: JTP-74057, JTP-78296, JTP-75303

Chemical and Structural Formula: GSK1120212B, a MEK 1/2 inhibitor, is a polycyclic, nitrogen containing heterocycle also possessing aromatic halide and amide functionality, and is a dimethyl sulfoxide solvate.

Molecular formula: C₂₆H₂₃FIN₅O₄C₂H₆OS

Molecular weight: 693.53

Physical Form: White to almost white solid

Solubility: Practically insoluble in the pH range of 2-8 in aqueous media.

8.2.3 Storage Requirements

Trametinib is to be refrigerated at 36-46°F. The recommended storage conditions, and expiry date where required, are stated on the product label, and on the storage and dosage cards dispensed to the patient with their medication.

8.2.4 Route of administration

The route of administration is oral.

9. CORRELATIVE STUDIES

9.1 Tumor pharmacodynamics (PD) evaluation (Tumor Biopsies pre-study and on-study)

9.1.1 Collection and Handling of Specimen(s): Fine needle aspiration (FNA) or core biopsy of tumor will be obtained at baseline and on C1D15 (+/- 5 days), for 7 patients in each arm of the study (14 patients total: "Biopsy cohort") who provide informed consent and have tumor lesions that are deemed by the study investigators to be accessible for biopsy. If funding permits, pre-study and on-study (C1D15) biopsies can be done in additional 6 patients on the trial. Optional biopsy/FNA will also be performed at progression in up to 5 patients in each arm of the FNA cohort who provide informed consent and who demonstrate initial radiographic response to therapy followed by radiographic progression. While these FNA/biopsies are invasive and will be done for research purpose, such procedures are routinely done for diagnostic purpose in clinical setting and are well tolerated in patients with thyroid cancer.

Biopsy/FNAs of accessible tumor will only be obtained under ultrasound or CT-guidance (unless palpable tumors) by medical personnel (e.g. cytologist, endocrinologist, surgeon, radiologist) with expertise in performing biopsy/FNA. Clinical trial research team member will be present bedside at time of biopsy to collect and process biopsy material. Detailed instructions describing this procedure will be included in a separate Study Lab Manual.

To assure that 10 evaluable paired FNA/biopsies are obtained from patients on each ARM of the study (total 20 patients), each participating center (total of 4 centers) will be required to enroll at least 5 patients who have paired biopsies. It is possible that 10 patients have pre-study biopsies but some of these patients might not be able to have 2nd on-study biopsy. Such case will be considered in-evaluable and additional patients will be recruited.

9.1.2 Shipping of Specimen(s): Frozen FNA samples will be batch shipped on dry ice to the Solid Tumor Translational Science (STTS) Resource at The Ohio State University Comprehensive Cancer Center along with the whole blood specimen and the frozen plasma samples collected for BRAF mutation testing. After the C2D1 collection time point. Shipping address and days of shipment details will be provided in the Lab Manual.

9.1.3 Site(s) Performing Correlative Study: Laboratory of [name] at Massachusetts General Hospital Cancer Center.

9.1.4 Methods for Analysis of Tumor Pharmacodynamics studies: Prior to staining, tumor biopsy samples will be thawed and deposited onto at least 3 glass slides by centrifugation (Cytospin), and briefly dried. Slides can be stored at 4°C covered in PBS until staining. The samples will be stained with antibodies to anti-thyroglobulin antibodies (thyroid cancer cells), CD45 (white blood cells), panCytokeratins, DAPI (nuclei), and one PD biomarker (pERK, NIS, pAKT, p-p70S6K or Ki67), followed by appropriate secondary antibodies, utilizing immunofluorescence staining protocols developed by [name] in [name]'s laboratory at Massachusetts General Hospital Cancer Center. Additional proteins that provide information on tumor biology or pharmacodynamics may be tested as deemed appropriate by investigators. Immunofluorescence based cellular analysis has the primary advantages over traditional immunohistochemistry of: multiplexed analysis (e.g. simultaneous staining with three-four markers); sensitivity to scant samples; and the potential ability to quantify the results. Stained slides will be scanned within 48 hrs of staining on a Duet-3 automated scanning system (Bioview). Candidate tumor cells will be automatically scored according to pre-defined thresholds (e.g. CD45-negative, DAPI-positive, Cytokeratin-positive), and then visually inspected to confirm both cell morphology and specificity of staining. For pharmacodynamic analysis of the FNAs, the distribution of fluorescence intensities corresponding to pERK, pAKT, p-p70S6K, NIS and Ki67 will be determined and compared in pre- and on-treatment samples. The percentage change of tumor cell pERK, pAKT, p-p70S6K, NIS and Ki67 levels from pretreatment levels (both mean fluorescence intensity and number of pixels above predefined thresholds as assessed by antibody staining) will be calculated. When patient-derived samples are analyzed, control cell lines, to consist of cultured BRAF-mutant thyroid cancer cells untreated or treated with the same agents, will be analyzed simultaneously and in

parallel. Day to day variations in assay performance will be accounted for by comparing the data derived from such control samples.

9.2 BRAF mutation quantification in circulating plasma DNA (Peripheral Blood pre-study, on-study and at progression):

9.2.1 Collection and handling of Specimen(s): All patients with a documented BRAF mutation at enrollment (up to 52 patients) will have 10 mL of whole blood collected in EDTA tubes on day 1 of each cycle for the first 6 cycles and then every other cycle (alternating with CT/MRI scan) after that while patients remain on study (C8D1, C10D1 etc.). If a patient goes off study due to disease progression, a sample will be collected at that time. Details on the processing of these samples are included in the Study Lab Manual.

9.2.2 Shipping of Specimen(s): Frozen plasma samples for cycles 1-2 will be shipped on dry ice to the Solid Tumor Translational Science (STTS) Resource at The Ohio State University Comprehensive Cancer Center along with FNA tumor biopsies (if applicable) and whole blood specimens. Specimens collected at cycle 3-7 will be held and batch shipped after cycle 7. The remaining samples will be stored at the individual sites and batched shipped either every 6 months or when the patient goes off study. Shipping address and days of shipment details will be provided in the Study Lab Manual.

9.2.3 Site(s) Performing Correlative Study: Solid Tumor Translational Science Resource (STTS) at the Ohio State University Comprehensive Cancer Center. For method validation, one sample of plasma may be shipped to Molecular Diagnostics Co.

9.2.4 Methods for Analysis of BRAF mutation quantification in circulating plasma DNA: DNA will be extracted from 1 mL of plasma, using the QIAamp Circulating Nucleic Acid kit (Qiagen) and quantitated using the Nanodrop 3300 Fluorospectrometer with PicoGreen (Thermo Scientific). The BRAF V600E mutation will be detected in purified plasma DNA by running a highly sensitive allele-specific TaqMan assay on the 7500 FAST Real Time PCR System (Applied Biosystems). DNA concentration will be normalized across samples using the delta-Ct value of the wild-type BRAF allele. Copy number of the BRAF V600E allele will be determined by comparing plasma samples results to a standard curve for BRAF V600E consisting of eight dilutions (100%, 50%, 20%, 10%, 1%, 0.1%, 0.02% and 0% mutated alleles) obtained by mixing purified wild-type and mutant linearized plasmid DNA.

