262 **BRAF V600E quantification in circulating plasma DNA:** Several investigators have demonstrated the ability to detect the BRAF V600E mutation in circulating plasma DNA samples from patients with BRAF^{V600E} mutant neoplasms, including melanoma (37-39) and thyroid cancer (40). With the emergence of new technology, it is now possible to develop highly sensitive assays to detect and obtain absolute concentrations of rare mutant alleles (41). We hypothesize that plasma levels of mutant BRAF alleles can be correlated to radiographic response as defined by RECIST, with improved sensitivity and specificity in comparison to traditional serologic correlates such as thyroglobulin (Tg), potentially allowing for the early detection of disease progression and resistance to therapy.

263 **Tumor mutation screening:** Third, we propose to study the potential mechanisms of resistance to BRAFi and MEKi in a subset of patients with initial response to therapy followed by subsequent progression. Several mechanisms of resistance to BRAF inhibitors have been described in melanoma, including BRAF-independent activation of the MAPK pathway (e.g., NRAS mutations), as well as upregulation of alternative signaling pathways that are independent of MAPK (e.g., PDGFR β , COT) (30, 31). However, it is unclear if these same pathways can be implicated in the development of resistance in thyroid carcinoma. Patterns of resistance are anticipated to differ in

patients treated with both BRAFi and MEKi as opposed to BRAFi alone: we expect that additional activating mutations of the MAPK pathway (e.g., NRAS) will be restricted to patients treated with BRAFi alone. IHC and tumor mutational screening will be performed at baseline and at progression as part of this analysis.

2.6.4 Predictive markers of response: Pre-clinical studies show that Trametinib responds better in tumors that have high levels of pERK expression. If we observe significant clinical response, we will evaluate levels of pERK, pAKT, pMEK expression in archival tumor samples. Alternative mechanism of funding will be sought.

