4.3 Cross-over from Arm A to Arm B

- At the treating physician's discretion, patients that experience disease progression on ARM A, may cross over from ARM A to ARM B. Each participating center needs to re-register the patient by contacting the coordinating center with the following data: Progressive disease documentation form (e.g. local Tumor Measurement Form)
- Reports of relevant CT/MRI scans including baseline and on study until progression

Patients that cross over to ARM B will not be eligible to participate in the Pharmacokinetics (PK) or the Pharmacogenetics (PGx) correlative studies.

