9.3 Tumor mutation screening/Mechanisms of drug-resistance (Tumor biopsy at Progression)

9.3.1 Collection and handling of Specimen(s): Tumor mutational analysis to determine mechanisms of drug-resistance will be performed in at least 5 patients

in each arm of the study (10 patients total) who 1) provide informed consent 2) demonstrate initial radiographic response followed by documented disease progression while on study and 3) have biopsy/FNA accessible tumors. DNA will be extracted from tissue taken at the time of progression and compared to DNA extraction from baseline tissue. Ideally these samples would be from patients enrolled in the "Biopsy cohort" for PD biomarker evaluation (section 9.1.1) in order to obtain the status of these biomarkers at progression; however, this may not be possible given the limited number of these patients. Baseline tissue can be from either the FNA samples taken at baseline (if the patient was in this cohort and sufficient material is available) or from archival formalin-fixed paraffin-embedded (FFPE) tumor tissue. FNA samples will be collected and processed as described in section 9.1.1 and 9.1.2. For archival tumor samples, please see section 9.4.

9.3.2 Shipping of Specimen(s):

From archival tumor sample shipment, please see section 9.4. Frozen FNA samples will be shipped on dry ice to the Solid Tumor Translational Science (STTS) Resource at The Ohio State University Comprehensive Cancer Center with any remaining frozen plasma samples for BRAF mutations analysis. Shipping address and days of shipment details will be provided in the Study Lab Manual.

9.3.3 Site(s) Performing Correlative Study: Solid Tumor Translational Science Resource (STTS) at The Ohio State University Comprehensive Cancer Center.

9.3.4 Methods for Analysis of Tumor Mutation/Mechanisms of resistance studies:

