| 2-mL blood per time point for pharmacokinetics (Section 9.5) ⁿ | | Please see Section 9.5 for details of time points | | | | | |
| Paraffin tumor block (Section 9.4) | X | | | | | | |

| 10-mL blood for BRAF mutations in circulating plasma (Section 9.2) | | X | | | X ^r | X (Cycles 3 and 5 only) | X Only if PD |
|---|---|---|--|---------------------------|----------------|----------------------------|-----------------|
| Tumor Pharmacodynamics Tumor Biopsy (Section 9.1) | X | | | X ⁱ +/- 5 days | | | |
| Tumor Mutation Screening Tumor Biopsy (Section 9.3) | | | | | | | X Only if PD |

- a. If pre-study labs (CBC/diff, Chemistry) are drawn within 14 days of study entry, such labs do not have to be repeated on C1D1.
- b. All on-study visits can be performed within +/-3 days. For cycles 8 to 18, please follow same schedule as for even and odd cycles as Cycles 2, 4, 6 or Cycles 3, 5, 7 respectively. Please review all footnotes as some testing is not required as frequently after 1st 6 cycles.
- c. Off-therapy evaluations are to be conducted within 4 weeks after last dose of study drug (s). Labs do not need to be repeated if done within 2 weeks.
- d. Sodium, Potassium, Chloride, Bicarbonate, Creatinine, BUN, Glucose, Calcium, Phosphorus, Total protein, Albumin, Total bilirubin, SGOT (AST), SGPT (ALT), Alkaline phosphatase, lactate dehydrogenase (LDH).
- e. Pregnancy test (sensitivity of at least 50 mIU/mL) will be performed for all women of childbearing potential before beginning study drug (s).
- f. CT or MRI scans as determined by investigators to assess the response per RECIST v1.1 criteria. CTs or MRIs with IV contrast are encouraged but will be done per investigator's discretion. Scans can be done within 7 days prior to day 1 of cycles 3, 5, 7 and subsequent odd number of cycles. If CT abdomen is negative at baseline, they only need to be repeated if clinically indicated during the study period.
- g. PET scans are performed only as clinically indicated at pre-study, every 8 weeks and off study as determined by treating physicians.
- h. Echo or MUGA will be done pre-study and every 2 cycles for 6 cycles and then every 4 cycles x 18 months and then only if clinically indicated. Scans can be done within 7 days prior to day 1 of cycles 3, 5, 7 and subsequent odd number of cycles.
- i. This can be done any time +/- 5 days from C1D15. Not required during C2D15 time point.

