- j. Patients on both ARMs must have a dermatologic exam to monitor and manage side effects on the skin.
- k. All patients must have ophthalmologic exam at pre-therapy. Patients randomized to or crossed over to ARM B (combination treatment arm) should have these as clinically indicated. Patients are required to have a standard ophthalmic exam performed by an ophthalmologist at baseline, and as clinically warranted per protocol's guidance (Refer to Section 6.2.2 for visual changes stopping criteria). The exam will include indirect fundoscopic examination, visual acuity (corrected), visual field examination, tonometry, and direct fundoscopy, with special attention to retinal abnormality that are predisposing factors for RVO or CSR. For patients with clinical suspicion of RVO or CSR, fluorescein angiography and/or optical coherence tomography are highly recommended.
- l. Each cycle start is allowed a +/- 3 day window
- m. Patients taking Antiplatelets or Anticoagulants need to have a CBC every 2 weeks for the first 4 months.
- n. Patients that cross over from ARM A to ARM B are not eligible for the PK or PGx correlative studies.
- o. All patients will receive a follow up phone call a week after each clinic visit for the first 4 months of treatment. The team will confirm with the patient that they are taking the correct amount of study medication, and that they have enough study medication to last until their next clinic visit.
- p. After the completion of the 18th cycle, visits will be extended to every 8 weeks. All exams, tests, and scans listed for the odd cycle visits will be completed.
- q. Electrocardiogram (EKG) will be done pre-study and every 2 cycles for 6 cycles and then every 4 cycles x 18 months and then only if clinically indicated.
- r. After completion of the 18th cycle, visits will be extended to every 8 weeks. BRAF research labs will be drawn at every other visit (every 16 weeks) and at time of progression.

Baseline evaluations are to be conducted within 4 weeks prior to start of protocol therapy. Four weeks (28 days) is considered one cycle. A member of the study team will be making a follow up phone call to each patient a week after each clinic visit for the first 4 months of treatment. The team will confirm with the patient that they are taking the correct amount of study medication, and that they have enough study medication to last until their next clinic visit.

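### Progression plasma and resistance-biopsy timing is tied to leaving study or therapy in 9.2.1 and the calendar but to progression elsewhere, and nothing secures either specimen before an Arm A patient crosses over

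*Combined protocol and SAP*

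**What the plan says.** **Plasma.** The heading of 9.2 describes collection as "Peripheral Blood pre-study, on-study and at progression". The operative sentence in 9.2.1 is narrower: "If a patient goes off study due to disease progression, a sample will be collected at that time". Routine draws fall on day 1 of cycles 1 to 6 and then at even cycles (8, 10 and so on), deliberately alternating with imaging. Footnote r of the Section 10 calendar covers visits after cycle 18: "BRAF research labs will be drawn at every other visit (every 16 weeks) and at time of progression".

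**Resistance biopsy.** Section 9.3.1 says that "DNA will be extracted from tissue taken at the time of progression and compared to DNA extraction from baseline tissue", in patients who responded and then progressed while still on study. Section 9.1.1 also places the optional biopsy at progression. The calendar row "Tumor Mutation Screening Tumor Biopsy" has a single tick, in the Off-therapy column and conditional on progression. Footnote c sets Off-therapy evaluations within 4 weeks after the last dose.

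**Crossover.** Under 4.3, at the physician's discretion, "patients that experience disease progression on ARM A, may cross over from ARM A to ARM B". Re-registration requires a progression form and scan reports. The only correlative work that 4.3 mentions is PK and PGx, from which these patients are excluded.

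**Purpose.** Section 2.6.3 expects that "additional activating mutations of the MAPK pathway (e.g., NRAS) will be restricted to patients treated with BRAFi alone". Section 2.6.2 hopes that plasma levels of mutant BRAF will reveal progression and resistance early.

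**The concern.** The resistance hypothesis contrasts tumours that escaped dabrafenib alone with tumours that escaped the combination. It needs Arm A tissue collected before any trametinib. If a crossover patient's progression specimen is taken when that patient finally stops therapy, it carries whatever was selected under both drugs, yet it may still be filed under the randomised arm. The plan has no rule for labelling specimens by regimen at collection. By contrast, 13.1.2 does keep post-crossover data out of the primary decision.

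Plasma raises a separate issue. For Arm A, the key event in the plasma time course is progression on dabrafenib alone, and a crossover patient may have no sample scheduled there. Neither specimen can be recovered once the combination has started.

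**Working it through.** The plan gives no figure for this point, so the check is mainly a comparison of passages.

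**1. Does an Arm A patient who crosses over meet the off-study or off-therapy trigger?** Section 5.5 states progression as a reason to end treatment for Arm B and offers crossover to Arm A patients. Section 5.7 removes patients from study when a 5.5 criterion applies. Arm B contains dabrafenib, so crossover is not a last dose of study drug in the ordinary sense. On the natural reading, neither trigger is met at Arm A progression. The documents do not state the status of a re-registered patient outright.

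**2. Where each source places the progression samples.**

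| Source | Plasma | Resistance biopsy |
|---|---|---|
| 9.2 heading | At progression | – |
| 9.2.1 | On going off study for progression | – |
| Footnote r (after cycle 18) | At progression | – |
| 9.1.1, 9.3.1, 2.6.3 | – | At progression |
| Calendar tick | Off-therapy column | Off-therapy column |
| 4.3 re-registration list | Not listed | Not listed |

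**3. Do routine plasma draws fill the gap?**
- Scan visits (footnote f): cycles 3, 5, 7, 9, 11, 13, 15, 17 and later odd cycles.
- Plasma draws up to cycle 18 (9.2.1 and calendar): cycles 1 to 6, then 8, 10, 12, 14, 16, 18.
- Overlap: cycles 3 and 5 only. From cycle 7 to cycle 17 there are six scan visits (7, 9, 11, 13, 15, 17) and none has a scheduled draw.
- The nearest earlier draw is day 1 of the preceding even cycle. A cycle is 28 days and the scan may be up to 7 days before day 1 of the odd cycle, so that draw precedes the scan by 28 − 7 = 21 to 28 days, ignoring the 3-day visit windows.

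**4. Which comparison does each specimen feed?** Section 2.6.3 uses tumour IHC and mutation screening at baseline and progression. The plasma assay in 9.2.4 detects BRAF V600E only. Late tissue therefore affects the resistance contrast, and missing plasma affects the 2.6.2 aim.

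**5. How much could late tissue matter?** This is an illustration on assumptions that are not in the documents. Suppose a resistance feature is present in a proportion p of tumours resistant to dabrafenib alone and is never detected in tissue taken after the combination. With k of the five Arm A specimens taken before crossover, the chance of seeing the feature at least once is 1 − (1 − p)^k.

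| k | p = 0.20 | p = 0.60 |
|---|---|---|
| 5 | 1 − 0.8^5 = 0.67 | 1 − 0.4^5 = 0.99 |
| 2 | 1 − 0.8^2 = 0.36 | 1 − 0.4^2 = 0.84 |
| 0 | 0 | 0 |

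**6. Is there a surplus of eligible patients?** Only responders who later progress qualify. At the design response rates in 13.1.3, an arm of 26 expects 26 × 0.15 = 3.9 or 26 × 0.35 = 9.1 responders. The binomial chance of at least five is 0.35 or 0.98 respectively. At the lower rate there is little room to replace a late specimen.

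**The case against.** The strongest reply is that every text section governing the biopsy says progression. Section 9.3.1 even requires progression while on study, and the calendar's correlative block refers the reader back to Section 9 and a Lab Manual. This stands. A reader might infer that the plan has Arm A crossover patients biopsied only after the combination, or that the resistance comparison is destroyed. The documents do not support either. The biopsy problem is a conflict between text and calendar, plus silence at crossover. Crossover is optional, and Arm A patients who do not cross over would be sampled appropriately on leaving therapy for progression.

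It is also true that plasma cannot damage the tumour contrast, because it is tested for V600E alone. Progressions found at the cycle 3 and 5 scans coincide with scheduled draws, and later ones have a draw three to four weeks earlier on dabrafenib alone. Section 9.2.2 mentions specimens from cycles 3 to 7, which hints at a cycle 7 draw, but neither 9.2.1 nor the calendar schedules one.

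Re-registration might restart the calendar, which would put a plasma draw on day 1 of the combination. The plan does not say so, does not state that such a draw precedes the dose, and would still place the resistance biopsy under Off-therapy.

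Finally, the work is exploratory. Section 13.4 specifies no between-arm test of resistance, and the primary endpoint is untouched. The Lab Manual may say more, but it is not among the documents. These points limit the stakes but do not remove the inconsistency.

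**Conclusion.** The concern holds as an inconsistency with a practical consequence. Read literally, 9.2.1 and the calendar schedule no plasma at Arm A progression for a crossover patient whose progression is found at any of the six odd-cycle scans from cycle 7 to cycle 17. This assumes that crossover is neither leaving study nor stopping therapy, and that the calendar does not restart. For the biopsy, a site following the calendar rather than 9.3.1 could sample after combination exposure. Each such specimen would be about one fifth of the Arm A resistance set.

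How many specimens would be late cannot be derived. The documents give no crossover rate, and it is unknown which source sites would follow. A reader might infer that most of the five Arm A specimens would be compromised, but that requires an assumed high crossover rate, late biopsy in every crossover patient and no replacement by patients who do not cross over. The supported conclusion is that the contrast in 2.6.3 could be blurred and the plasma aim in 2.6.2 weakened. The change should be made because it is cheap and the specimens are irrecoverable.

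**What to change.** - Reconcile 9.2.1 and the calendar with the 9.2 heading, footnote r, 9.1.1 and 9.3.1 by defining both the plasma sample and the optional biopsy by first progression on the assigned regimen.
- Add to the 4.3 re-registration list that the plasma sample, and the biopsy where the patient has consented, are collected after documented Arm A progression and before the first combination dose.
- Label each specimen by the regimen being taken at collection, and record any taken after crossover as second progression.
- State that only pre-crossover Arm A specimens enter the between-arm resistance comparison.

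The cost is a wording amendment and a short addition to the re-registration checklist. The 10 mL tube and the optional biopsy are those already planned. The one real burden is fitting them between the progression scan and the start of crossover.
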